### **3.3 Rationale For Study Design**

Pharmaceutical agents that target VEGF have revolutionized the management of neovascular AMD. VEGF-A is a diffusible cytokine that stimulates angiogenesis and vascular permeability. Clinical blockade by intravitreal injection of ranibizumab is remarkably effective against choroidal neovascularization (CNV) in AMD patients.

The efficacy of anti-VEGF therapy in AMD was initially demonstrated with the modified antibody fragment ranibizumab in two landmark trials, ANCHOR and MARINA. For the first time, patients with CNV secondary to AMD experienced an average visual improvement with over 90% of eyes losing less than 15 letters and about 30% of eyes gaining significant vision. Ranibizumab was FDA approved on June 30, 2006.

Since then we have learned a tremendous amount about the clinical utility of intraocular VEGF blockade. Despite these advances, a major clinical controversy regarding exudative AMD management remains today: what is the optimal treatment approach to maximize visual outcome and minimize treatment burden for patients and the health care system?

#### **Monthly vs Extended Fixed Interval Schedules vs PRN Treatment**

Both MARINA and ANCHOR employed monthly ranibizumab dosing. While this treatment approach yielded exceptional results with sustained visual gains over 2 years, monthly doctor visits are often impractical and difficult for patients and their caregivers. Therefore, large prospective trials have evaluated 2 main alternative treatment approaches in an attempt to decrease the treatment burden while maintaining visual gains: fixed interval treatments with less than monthly dosing, and pro re nata (PRN) treatment.

Prior attempts at fixed interval schedules employing less than monthly treatments have resulted in disappointing visual outcomes. For example the PIER study, a phase IIIb, multicenter, randomized, controlled trial compared sham injections to ranibizumab monthly for 3 months and then quarterly. In stark contrast to the results of MARINA and ANCHOR, while visual outcomes were statistically better than the sham treated control group, the visual acuity improvement observed at month 3 was lost by month 12, with patients losing a mean of -1.6, and -0.2 letters in the 0.3 mg and 0.5 mg ranibizumab groups respectively. Similarly suboptimal outcomes were seen with the EXCITE and SAILOR results which employed similar quarterly dosing strategies without success.

Importantly, however, subgroup analysis of PIER patients who showed no recurrence of exudative disease activity after the first 3 months of treatment on quarterly dosing showed sustained visual gains compared to visual losses observed in patients who showed persistent exudative disease activity after the first 3 months of treatment (Brown D.M. et al RETINA. In press). It is likely that the prolonged and recurrent episodes of retinal edema observed in the majority of under-treated quarterly treated patients directly contributed to their poor visual outcomes. Therefore, it seems that while under-treatment of active exudative disease in the setting of wet AMD leads to suboptimal visual outcomes, not all patients require monthly dosing to achieve optimal visual outcomes; namely, those wet AMD patients without active exudative disease may be able to have a reduced treatment burden while maintaining their visual gains.

In comparison to fixed extended dosing, some strict prospective studies of PRN treatment approaches have yielded positive results that have appeared to be in the range of vision gains demonstrated in the MARINA and ANCHOR established standard. PrONTO was a 2-year, prospective, open label, non-comparison single arm study of 40 eyes, in which patients received 3 consecutive monthly intravitreal injections of ranibizumab followed by monthly evaluation and retreatment if certain clinical criteria were fulfilled. At month 24, mean visual acuity improved 11.1 letters with an average of 9.9 injections. One of the important observations from PrONTO was the wide range of necessary injections among patients; 3 patients required only the minimum possible number of treatments, 3; and 2 patients required the maximum possible number of injections, 24.

In the much larger and prospectively randomized CATT trial, analysis of pooled data including both ranibizumab and bevacizumab treated eyes suggested that monthly fixed dosing may be preferable to PRN therapy. In respect to avoiding vision loss the best performing group (monthly ranibizumab) had 7% 3-line losers from baseline compared to the worst (as needed bevacizumab), which experienced 12% 3-line losers. The vision losses seen with PRN therapy may be secondary to PRN regimen's decreased

anatomic efficacy, which led to more persistent retinal fluid compared to monthly treatment (75%-85% vs 52-67%,  $P < 0.0001$ ) and an increase in baseline CNVM lesion size by 1.9 to 3mm^2 vs -0.4 to 1.6mm^2 with monthly treatment ( $P = 0.0003$ ). Also emphasizing the challenges of PRN dosing, half of patients initially assigned to monthly treatment were reassigned to PRN treatment after 1 year; these re-assigned PRN patients lost between 1.5 and 3 mean letters more than the patients who maintained monthly dosing ( $P = 0.03$ ).

Similarly, results of the phase III, multicenter, randomized controlled HARBOR trial also supported the superiority of monthly fixed dosing compared to strict monthly monitoring with PRN treatment. While both the 0.5mg and 2.0mg ranibizumab PRN arms resulted in clinically meaningful improvements in vision, neither arm met the prespecified primary endpoint of statistical noninferiority compared with 0.5mg ranibizumab monthly injections.

### **Treat and Extend Treatment**

Just as every human is genetically distinct, so too it appears is the clinical response to anti-VEGF treatments in the setting of wet AMD, underscoring the concept of individualized dosing regimens. Supporting this concept, intraocular levels of VEGF vary among patients with phenotypically similar diseases over a wide range of diagnoses.

A treat and extend protocol starts with monthly injections until signs of exudation have resolved with clinical and SD-OCT confirmation. The interval between visits is then sequentially lengthened by 1 to 2 weeks as long as there are no signs of recurrent exudation. Treatment is rendered at every visit but the time between visits is individualized based on a patient's response to treatment. When recurrent disease is detected, the treatment interval is reduced. The goal is to maintain an exudation-free macula with the fewest number of office visits, tests and injections.

Such a protocol was first described in 2007. Since then, four reports have described retrospective analyses of patients treated with varying types of treat and extend protocols. For example, Gupta et al reported a retrospective analysis of 92 eyes with wet AMD treated with ranibizumab according to a treat and extend protocol. After a mean follow-up of 1.5 years, non-refracted visual acuity outcomes demonstrated 32% of patients gaining 3 lines of Snellen visual acuity and 96% of patients losing less than 3 lines of vision. Similar to the variability of required treatments reported in PrONTO a wide range of required treatment frequencies was observed. After an exudation-free macula was achieved, 42 eyes (46%) demonstrated no recurrent exudation while 7 eyes (8%) showed persistent exudation at every visit, requiring monthly dosing throughout the study period. These retrospective studies consistently report beneficial outcomes; however evaluations, follow-up intervals and endpoints were not standardized or consistent.

Most visual acuity data have shown that monthly dosing produces superior anatomic and visual acuity outcomes compared to both fixed interval dosing employing less than monthly treatments and monthly visits with PRN treatment upon detection of exudative disease activity. Nonetheless, individualized treatment protocols are intuitive and rational based on multiple clinical observations. With the 2-year CATT data demonstrating that PRN therapy results in significantly less VA gain, it is likely that most evidence-based treatment protocols will abandon the PRN approach. It is likely that the CATT data will convert more clinicians to switch to the prospectively untested “treat-and-extend” regimen or monthly therapy. In retrospective data, such treat and extend protocols significantly reduce the burden of care for patients and physicians, decrease the cost of care delivery and result in equivalent visual outcomes. The time is ripe for a large, prospective treat and extend protocol for exudative AMD management.

### **Rational for Year 3**

To determine if subjects who are dry and have been extended to a 12-week interval can maintain their dry macular status without continued ranibizumab injections.

To determine if subject who are dry on monthly dosing can maintain their dry macular status without continued ranibizumab injections.

To continue to attempt to extend and optimize treatment intervals for subjects with less than 12-week intervals between injections in the TREX arm.

## **3.4 OUTCOME MEASURES**

### **3.4.1 Primary Outcome Measure**

- Mean change in ETDRS visual acuity from baseline to weeks 24-28, baseline to weeks 48-56, baseline to weeks 72-82, baseline to week 104, baseline to weeks 128-132 and baseline to week 156.

### **3.4.2 Secondary Outcome Measures**

- Incidence and severity of adverse events (ocular and non-ocular).
- Total number of intravitreal injections required from baseline through weeks 48-57 (week closest to week 52), baseline through week 104 and baseline through week 156.
- Total number of office visits and imaging studies performed from baseline through weeks 24-28 (week closest to week 26), baseline through weeks 48-56 (week closest to week 52), baseline through weeks 72-82 (week closest to week 78), baseline through week 104, baseline through weeks 128-132 (week closest to week 132) and baseline through week 156.
- Percentage of subjects with persistent active exudation on SD-OCT from baseline through weeks 48-57 (week closest to week 52), baseline through week 104 and baseline through week 156.

- Percentage of subjects with persistent leakage on fluorescein angiography from baseline through weeks 24-28, baseline to weeks 48-56, baseline to weeks 72-82, baseline to week 104, baseline to weeks 128-132 and baseline to week 156.
- CNVM lesion size at baseline, compared to baseline to weeks 24-28, baseline to weeks 48-56, baseline to weeks 72-82, baseline to week 104, baseline to weeks 128-132 and baseline to week 156, as determined by fluorescein angiography.
- Mean change in central foveal thickness by SD-OCT from baseline to weeks 48-57, baseline to week 104 and baseline to week 156.
- Mean change in BCVA by ETDRS letter score from baseline through weeks 24-28, baseline through weeks 48-56, baseline through weeks 72-82, baseline to week 104, baseline through weeks 128-132 and baseline to week 156.

### Endpoint Visits:

Few completed prospective trials have employed a treat and extend protocol. Therefore, there is little data regarding optimal endpoint usage. These endpoints will allow comparison of data from each cohort.

1. **Floating Endpoints** (also known as the Biological Endpoints): Analyses will be performed between weeks 24-28, between weeks 48-57, between weeks 72-82, week 104, between weeks 128-132 and week 156 (range to be determined by timing of last injection). If more than one possible endpoint exists, the time point closest to week 26, week 52, week 78, week 104, week 130 or week 156 will be used. This will be applied to both Cohort A and B, but likely to be most important for Cohort B. All endpoints are measured 4 weeks following the last injection.
2. **Hard Endpoints**: analyses will be performed at week 52 (day 365 $\pm$  7 days), week 104 (day 730  $\pm$  7 days) and week 156 (day 1095)

### 3.5 SAFETY PLAN

The safety assessments to be conducted for this study are listed in Section 4.5.

The safety and tolerability of intravitreal ranibizumab injections have been investigated in previous Phase I, I/II, III, and IIIb studies in AMD, RVO and DME trials. Potential safety issues associated with the route of administration or the pharmacology of ranibizumab in the study population include decreased BCVA, intraocular inflammation intraocular infection, transient and/or sustained elevation of intraocular pressure (IOP), cataract development or progression, retinal or intravitreal hemorrhage, macular edema, retinal break or detachment, and arterial thromboembolic events (ATEs). Safety will be assessed by visual acuity, ophthalmic examinations, intraocular ocular pressure measurements, fluorescein angiograms, OCT, adverse event documentation and vital signs.

To minimize the risks of intraocular injections, all injections will be performed employing surgical sterile techniques as described in Appendix B. Intraocular pressure will be measured before and 30 minutes ( $\pm$  15 minutes) after each ranibizumab injection. Any subject who develops significantly raised intraocular pressure ( $\geq$  30 mmHg) at any time during the study should be monitored according to the physician's clinical judgment and may undergo additional measurements of intraocular pressure beyond those specified in the protocol

Study drug administration will be held for subjects who experience certain ocular events or infection events. In the event any subject develops an adverse event in the study eye that is considered by the physician to be severe in intensity, serious consideration should be given to withdrawing the subject from the study.

All adverse events will be reviewed by the PI or designated sub investigators on an ongoing basis.

### **3.6 COMPLIANCE WITH LAWS AND REGULATIONS**

This study will be conducted in accordance with current U.S. Food and Drug Administration (FDA) Good Clinical Practices (GCPs), and local ethical and legal requirements.

## **4. MATERIALS AND METHODS**

### **4.1 SUBJECTS**

#### **4.1.1 Subject Selection**

60 subjects from approximately 4 sites in the United States will be enrolled. Eligible subjects who have provided informed consent will be screened for eligibility before the initiation of any study procedures. Screening evaluations may be performed at any time within the 14 days preceding Day 0. Subjects must have wet macular degeneration secondary to age, with no prior treatment; with disease activity seen on SD-OCT. Subjects can only have one eye in the study, if both eyes are eligible to be in the trial the investigator will determine which eye will be in the study (study eye). Genentech will supply drug for the non-study eye (fellow eye) if needed. Subjects will be randomized in a 1:2 ratio so that:

- 20 subjects will be randomized to the monthly arm (Cohort A)
- 40 subjects will be randomized to the TREX arm (Cohort B)

\*See Appendix A, the study flow chart, for screening assessments.

#### **4.1.2 Inclusion Criteria**

Subjects will be eligible if the following criteria are met:

- Ability to provide written informed consent and comply with study assessments for the full duration of the study
- Age  $\geq$  50 years

#### Patient-related considerations

- For sexually active women of childbearing potential, agreement to the use of an appropriate form of contraception (or abstinence) for the duration of the study
- Although no birth control method is 100% effective, the following are considered effective means of contraception: surgical sterilization, use of oral contraceptives, barrier contraception using either a condom or diaphragm with spermicidal gel, an intrauterine device, or contraceptive hormone implant or patch. A patient's primary care physician, obstetrician, or gynecologist should be consulted regarding an appropriate form of birth control.
- Ability and willingness to return for all scheduled visits and assessments

#### Disease-related considerations

- Any CNVM lesion (Occult, Minimally Classic or Classic) (i.e., leakage on fluorescein angiography or subretinal, intraretinal activity on SD-OCT) secondary to age-related macular degeneration.
- Best corrected visual acuity in the study eye, using ETDRS testing, between 20/32 and 20/400 (Snellen equivalent), inclusive.
- Only one eye will be enrolled in the Study. If both eyes are eligible study investigator will select the eye for entry.
- The total area of subretinal hemorrhage and fibrosis must comprise less than 50% of the total lesion.
- Clear ocular media and adequate pupillary dilation to permit good quality fundus imaging.

#### **4.1.3 Exclusion Criteria**

Subjects who meet any of the following criteria will be excluded from this study:

##### General Exclusion Criteria

- Pregnancy (positive pregnancy test) or lactation
- Premenopausal women not using adequate contraception. The following are considered effective means of contraception: surgical sterilization or use of oral contraceptives, barrier contraception with either a condom or diaphragm in conjunction with spermicidal gel, an IUD, or contraceptive hormone implant or patch.
- Any other condition that the investigator believes would pose a significant hazard to the subject if the investigational therapy were initiated
- Participation in another simultaneous medical investigation or trial

##### Ocular Exclusion Criteria

##### Prior Ocular Treatment

- History of vitrectomy surgery, submacular surgery, or other surgical intervention for AMD in the study eye

- Prior treatment with Visudyne®, external-beam radiation therapy, or transpupillary thermotherapy (TTT) in the study eye at a fluence equal to 100%, any fluence lower than 100% is permitted.
- Any Previous intravitreal drug delivery (e.g., intravitreal corticosteroid injection, anti-angiogenic drugs including ranibizumab, or device implantation) in the study eye.

#### CNV Lesion Characteristics

- Subretinal hemorrhage in the study eye that involves the center of the fovea, if the size of the hemorrhage is either > 50% of the total area of the lesion or > 1 disc area (2.54 mm^2) in size
- Subfoveal fibrosis or atrophy in the study eye
- CNV in either eye due to other causes, such as ocular histoplasmosis, trauma, or pathologic myopia

#### Concurrent Ocular Conditions

- Retinal pigment epithelial tear involving the fovea in the study eye
- Any concurrent intraocular condition in the study eye (e.g., cataract or diabetic retinopathy) that, in the opinion of the investigator, could either: Require medical or surgical intervention during the 24-month study period to prevent or treat visual loss that might result from that condition; or if allowed to progress untreated, could likely contribute to loss of at least 2 Snellen equivalent lines of BCVA over the 24-month study period.
- Active intraocular inflammation (grade trace or above) in the study eye
- Current vitreous hemorrhage in the study eye
- History of rhegmatogenous retinal detachment or macular hole (Stage 3 or 4) in the study eye
- Active infectious conjunctivitis, keratitis, scleritis, or endophthalmitis in either eye
- Aphakia or absence of the posterior capsule in the study eye
- Intraocular surgery (including cataract surgery) in the study eye within 2 months preceding Day 0
- Uncontrolled glaucoma in the study eye (defined as IOP ≥ 30 mmHg despite treatment with anti-glaucoma medication)
- History of glaucoma-filtering surgery in the study eye
- History of corneal transplant in the study eye
- History of pars plana vitrectomy

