#### **3.2 OVERVIEW OF STUDY DESIGN**

This trial will compare the results of 2 cohorts, with different treatment intervals, to assess the safety, tolerability and efficacy of IVT of ranibizumab for the treatment of wet AMD. Specifically, this trial will evaluate the ability to reduce the amount of visits and IVT ranibizumab treatments needed all while maintaining an exudation-free macula. Subjects in both cohorts will be followed for a total of 156 weeks.

**Cohort A** (control arm, monthly, n=20) Subjects will receive monthly treatment of IVT 0.5 mg ranibizumab from Day 0 to week 100. Monthly treatment is defined as every 28 days (±7 days). Dosing should not occur earlier than 21 days after the previous treatment.

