#### **4.8.3 Efficacy Analyses**

##### **Primary Outcome Measure**

The primary outcome measure for safety, tolerability and efficacy are:

- Mean change in ETDRS visual acuity from baseline to weeks 24-28, baseline to weeks 48-56, baseline to weeks 72-82, baseline to week 104, baseline to weeks 128-132 and baseline to week 156.

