

APPENDIX Year 1 T-REX/ Treat and Extend for Wet AMD/(Monthly)Control Arm/Cohort 1

Week (±7 days)	Screen	Day	Day 7	4	8	12	16	20	24	28	32	36	40	44	48
Visit	Visit	Visit	Visit	Visit	Visit	Visit	Visit	Visit	Visit	Visit	Visit	Visit	Visit	Visit	Visit
Sign IFC	X														
Medical/Oph HX	X														
Vital Signs	X	X	X	X	X	X	X	X	X	X	X	X	X	X	X
Interval History (AE & Con Meds)	X	X	X	X	X	X	X	X	X	X	X	X	X	X	X
Indirect/Slit Lamp Exam	X	X	X	X	X	X	X	X	X	X	X	X	X	X	X
IOP (Pre & Post Injection)	X	X	X	X	X	X	X	X	X	X	X	X	X	X	X
Visual Acuity (ETDRS)	X	X	X	X	X	X	X	X	X	X	X	X	X	X	X
SD-OCT	X	X	X	X	X	X	X	X	X	X	X	X	X	X	X
Auto Fluorescence	X	X	X	X	X	X	X	X	X	X	X	X	X	X	X
Fundus Photo/ FA	X								X						
CNVM Measurement	X								X						
Study Drug Injection		X		X	X	X	X	X	X	X	X	X	X	X	X
Telephone Safety check (±3 days)		X													

\*\*\*\* Additional measurements will need to be scheduled 4 weeks post injection within the "quarterly report" windows defined below. In the event that two possible additional sessions (4 weeks post injection) can be scheduled within a quarterly window, schedule the session, which falls closest to month 6 (week 24), month 12 (week 52), month 18 (week 78), month 24 (week 104), month 30 (week 128) or month 36 (week 156) mark.

Ye T-REX/ Treat and Extend for Wet AMD/(Monthly) Control Arm/Cohort 1 (cont'd)

Week (±7 days)	52	56	60	64	68	72	76	80	84	88	92	96	100	104
Visit	Visit 16	Visit 17	Visit 18	Visit 19	Visit 20	Visit 21	Visit 22	Visit 23	Visit 24	Visit 25	Visit 26	Visit 27	Visit 28	Visit 29
Vital Signs	X	X	X	X	X	X	X	X	X	X	X	X	X	X
Interval History (AE & Con Meds)	X	X	X	X	X	X	X	X	X	X	X	X	X	X
Indirect/Slit Lamp Exam	X	X	X	X	X	X	X	X	X	X	X	X	X	X
IOP (Pre & Post Injection)	X	X	X	X	X	X	X	X	X	X	X	X	X	X
Visual Acuity (ETDRS)	X	X	X	X	X	X	X	X	X	X	X	X	X	X
SD-OCT	X	X	X	X	X	X	X	X	X	X	X	X	X	X

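### The exclusion for concurrent eye disease looks ahead 24 months, but follow-up lasts 156 weeks and two of the six primary time points fall after month 24

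*Combined protocol and SAP*

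**What the plan says.** The exclusion in Section 4.1.3, under Concurrent Ocular Conditions, has two limbs, both left to the investigator's opinion. The first concerns a condition in the study eye that could "Require medical or surgical intervention during the 24-month study period". The second concerns a condition that, left untreated, "could likely contribute to loss of at least 2 Snellen equivalent lines of BCVA over the 24-month study period". Cataract and diabetic retinopathy are the examples given.

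Section 3.2 gives a different length of study: "Subjects in both cohorts will be followed for a total of 156 weeks". Sections 3.1 and 4.2 also run to 156 weeks.

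The primary outcome is mean change in ETDRS visual acuity at six time points. The list in Section 3.4.1 ends with "baseline to week 104, baseline to weeks 128-132 and baseline to week 156", and Sections 2.1 and 4.8.3 give the same six. The note under the first monthly-arm table in the schedule of events supplies the conversion from months to weeks: "month 24 (week 104), month 30 (week 128) or month 36 (week 156) mark".

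**The concern.** The criterion is there to keep out eyes whose acuity would change for reasons other than AMD while the study is measuring it. It can do so only for the period it names. That period is called the study period, yet it ends a year before the study does.

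Consider an eye with early cataract that the investigator expects to need surgery, or to cost two lines, at about month 30 and not before month 24. This criterion does not exclude it, but its acuity at weeks 128-132 and week 156 enters a primary outcome. Progression would pull that eye's change score down, and surgery could push it up. With 20 and 40 subjects per arm, a few such eyes can visibly move a year-3 mean. Section 4.8.4 analyses available cases only, and the statistical section has no rule for intraocular surgery or media change.

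**Working it through.** **Inputs**
- Look-ahead: 24 months, both limbs (Section 4.1.3).
- Follow-up: 156 weeks, both cohorts (Section 3.2).
- Primary time points: weeks 24-28, 48-56, 72-82, 104, 128-132 and 156 (Sections 2.1, 3.4.1, 4.8.3).
- Conversion: month 24 = week 104, month 36 = week 156 (schedule of events).
- Arm sizes: 20 in Cohort A, 40 in Cohort B (Section 4.1.1).
- Letters per chart line: 5, so 2 lines = 10 letters (Appendix F, section 1.2).
- Share of eyes affected in year 3: not in the documents. Assumed at 5%, 10% and 20%.

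**Step 1. Does the stated study length reproduce?** By calendar, 24 × 30.4375 / 7 = 104.4 weeks, and 156 × 7 / 30.4375 = 35.9 months. Both agree with the document's own conversion. A 24-month study period therefore ends at week 104 and does not match 156 weeks.

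**Step 2. What lies beyond the look-ahead?**
- Time: 156 − 104 = 52 weeks, and 52 / 156 = 33% of follow-up.
- Primary time points after week 104: weeks 128-132 and week 156, so 2 of 6.

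With a 156-week look-ahead both counts fall to zero. They measure the gap in the wording, not an effect on the results.

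**Step 3. How large could the effect be?** Suppose a share p of eyes in each arm loses exactly 10 letters in year 3 from another condition, independently, with all 60 subjects observed.
- Shift of each arm's mean = 10 × p letters, downward.
- Expected between-arm difference = 10p − 10p = 0, because allocation is random.
- Chance SD of the difference = 10 × √[p(1 − p)(1/20 + 1/40)] letters, where 1/20 + 1/40 = 0.075.

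| Assumed p | Shift in each arm | Chance SD of difference | 95% range (±1.96 SD) |
|---|---|---|---|
| 5% | 0.5 | 10 × √(0.0475 × 0.075) = 0.60 | ±1.2 |
| 10% | 1.0 | 10 × √(0.09 × 0.075) = 0.82 | ±1.6 |
| 20% | 2.0 | 10 × √(0.16 × 0.075) = 1.10 | ±2.1 |

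These figures illustrate losses only; gains after surgery would work the other way. The documents give no SD, effect size, margin or power for the 60 subjects, so the extra noise cannot be set against a planned precision.

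**The case against.** Three objections carry weight.

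**Such eyes are not simply eligible.** A reader might infer that any eye expected to lose vision in year 3 gets in. The documents do not support that. The first limb asks only whether intervention could be needed, a low threshold that would already catch many eyes close to surgery. Section 4.1.2 requires clear media for good imaging. Section 4.1.3, under Concurrent Systemic Conditions, excludes other disease or findings that might affect interpretation of the results, with no time limit. These narrow the group to conditions visible at screening and foreseen to matter after month 24 but not before. They do not close the gap: the media requirement describes the eye at entry, and the catch-all is discretionary, sets no horizon and does not name eye disease.

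**A one-arm calculation misleads.** Two affected eyes in Cohort A would move that arm's mean by 2 × 10 / 20 = 1.0 letter, and a reader might take this as the distortion of the comparison. Under 1:2 allocation, two such eyes in A correspond to an expected four in B, which shift that mean by the same 4 × 10 / 40 = 1.0 letter. If only two existed among the 60, the chance that both fell in A is (20/60) × (19/59) = 11%. Only chance imbalance remains.

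**The remedy has limits.** No entry criterion prevents cataract that arises on study. Section 3.5 lists cataract development or progression among the potential safety issues of the drug or the injections, and the arms may differ in injection count. Leaving out visits after surgery or media change would condition on a post-randomisation event that treatment may cause. Section 3.3 also gives year 3 a separate rationale, so the 24-month text may date from a two-year design. That is an inference. If enrolment had closed by then, new wording would not change who is in the trial.

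**Conclusion.** The inconsistency is real and stands in the current text: both limbs give the study period as 24 months, while the design section gives 156 weeks. One third of follow-up and two of six primary time points lie outside the look-ahead.

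The consequence is minor. It consists of shifted year-3 means, added noise and possible chance imbalance between 20 and 40 subjects. The chance SD of the difference is about 0.6 to 1.1 letters if 5% to 20% of eyes lost 10 letters. That range is an assumption, and nothing in the documents indicates how many such eyes to expect.

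A reader might infer a systematic bias between regimens. The documents do not support this: affected eyes are randomised like the rest, and the expected difference from this source is zero. The comparison of monthly with treat-and-extend dosing through week 104 lies within the 24 months and is unaffected.

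**What to change.** Reconcile Section 4.1.3 with Sections 3.2, 3.4.1 and 4.8.3 so that both limbs refer to the full 156-week study period. This is an edit in two places, and its cost is slightly fewer eligible subjects.

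If subjects were enrolled under the 24-month text, also:
- record intraocular surgery and media change in the study eye throughout follow-up, because surgery before week 104 also carries into the year-3 values;
- report these events by arm;
- keep year-3 BCVA on all available data as the main result;
- label any analysis without post-surgery visits as supportive, stating that cataract may be related to treatment.

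Slit-lamp examination is already scheduled at every visit (Section 4.5.1), so the added cost is a data field and one table.
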